Aim 3: To assess the impact of peer mentoring on LBD caregiver mentees.

H3: Family caregivers of patients with LBD will demonstrate increased caregiving mastery, LBD knowledge, and improved social support, after 16 weeks of structured peer mentoring.

This work will identify key features of caregiving mastery and support in LBD, refine and validate a caregiver support toolkit, and test the impact of a theory-driven intervention to mitigate adverse caregiver outcomes.

I.b. Background

PD affects nearly one million individuals in the US, with a 77% projected increase in prevalence by 2030²⁴. With increasing age and PD duration, the prevalence of PD Dementia (PDD) approaches 70%^{25,26}. Conversely, 4.2 to 7.5% of *all* individuals with dementia will be diagnosed with DLB²⁷. DLB and PDD differ in chronology but share similar underlying pathology and neuropsychiatric features—particularly, depression, anxiety, delusions, and hallucinations—hence the umbrella classification of LBD²⁸. As LBD progresses, symptoms increase in number and severity, quality of life worsens, and hospitalizations and caregiver strain increase^{3,29,30}.

The leading causes of hospitalization in LBD are falls, urinary incontinence or infection, dehydration, and neuropsychiatric changes, many of which are preventable or treatable at home if recognized and addressed promptly¹². An independent but related risk factor in both hospitalization and institutionalization in LBD is caregiver strain^{4,8,9}. Once hospitalized or institutionalized, people with LBD suffer excessive iatrogenic morbidity and mortality¹². Despite overwhelming evidence linking caregiver strain to both acute healthcare utilization and to adverse caregiver health consequences³², and despite unmet needs for prognostic counseling and education for LBD caregivers, few interventions have targeted caregiver strain in this population^{31–33}.

[figure not shown]

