Mentors will attend one 6-7 hour training session, either held in-person at Rush University or a via passwordprotected videoconferencing application, such as Zoom. Study expectations and logistics will be reviewed with each potential mentor prior to the training session via phone. For all subjects, regardless of whether they attend an online or in-person training session, the informed consent process will take place online via REDCap prior to the training session date. In this way, participants can contact the study team with any questions or concerns prior to the training session. After participants have read the online consent form and indicated they are willing to participate, they will complete capacity assessment questions (see Section V.b.) to ensure understanding of the consent process.

Individuals may refuse to participate in the study and leave the peer mentor training session at any time. At the beginning of the training session, baseline data will be collected either via printed pen-and-paper assessments, or via online surveys (demographics, mentoring preferences, mastery scale, LBD knowledge test, Dementia Attitudes Scale (DAS); see Section III.d. for details). Next, mentors will receive training regarding topics including active listening, mentoring, goal-and boundary-setting, an overview of LBD, risk factors for hospitalization, impact on caregiver, practical approaches to symptom management, and caregiving issues. The study team will then present the new PERSEVERE curriculum and accompanying handbook. The study team will solicit questions and lead role-play conversations. Finally mentors will complete post-training assessments (mastery scale, LBD knowledge test, DAS) and will receive a training stipend (either directly from study team members if in-person, or mailed/emailed if completing training virtually).

III.c. Aim 3: Subject Identification, Recruitment, Consenting and Study Procedures

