Once Aim 2 (above) is complete and 36 mentors have been trained, caregiver mentees will be matched with mentors by relationship to LBD patient, then by sex and age, as much as possible. Mentor and mentee preferences expressed in the mentoring preferences survey will be honored to the extent that the study team is able given the available mentor and mentee participants. The study team will contact mentees once a match is available for them. First, the study team will direct the mentee to complete baseline primary and secondary outcome assessments online via REDCap, including: mastery scale¹⁹, LBD knowledge test, loneliness scale⁴¹, Short Zarit Burden Interview (ZBI-12)⁴², Hospital Anxiety and Depression Scale (HADS)⁴³, Geriatric Depression Scale – Short Form (GDS-SF)⁴⁴, and Dementia Attitudes Scale (DAS)⁴⁵ in order to obtain their pre-intervention baseline. The study team will then provide the mentee with contact information for their mentor, and caregivers will be mailed the PERSEVERE handbook.

Mentor-mentee pairs will then begin the 16-week peer mentor program. During this time, pairs will be expected to speak for ≥15-30 minutes weekly, and to review that week's PERSEVERE topics in the handbook before or during each call to facilitate meaningful conversations. Discussions are not scripted and will not necessarily be limited to that week's topics, at the discretion of the participants. Mentors and mentees will complete online study diaries every 2 weeks, assessing intervention fidelity. Up to 3 email reminders will be sent and/or up to 3 phone calls attempted to complete each study diary. Diary entries will include information such as call frequency, duration, topics discussed, and concerns. At the Week 8 or Week 10 survey, all mentees and those mentors who are still actively caregiving for a loved one with LBD will complete the Parkinson's Disease Carer Questionnaire (PDQ-Carer), a novel measure of PD-specific caregiver quality of life. Mentors will participate in 4 recorded monthly conference calls to share successes, challenges, and feedback, and to ask questions of and be supported by the study team.

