Upon completion of the 16-week mentor program, mentors and mentees will be sent a link to complete postmentoring assessments online (mentors: mastery scale, LBD knowledge test, DAS, PDQ-Carer; mentees: mastery scale, LBD knowledge test, loneliness scale, ZBI-12, HADS, GDS-SF, DAS, PDQ-Carer, and fall frequency and healthcare utilization of their loved one; see Figure 3).

	Aim 2 - Mentor Training	Aim 3 – PERSEVERE Pilot
Primary	 Mastery scale¹⁹ 	Mastery scale
Outcomes	Multiple-choice LBD	 LBD knowledge test
	knowledge test	 Loneliness scale⁴¹
Secondary	Mastery Scale (after	 Short Zarit Burden Interview (ZBI-12)⁴²
Outcomes	mentoring)Dementia Attitudes Scale	 Hospital Anxiety and Depression Scale (HADS)⁴³
	 (DAS)⁴⁵ Parkinson's Disease Carer 	 Geriatric Depression Scale – Short Form (GDS- SF)⁴⁴
	Questionnaire (PDQ-Carer)	• DAS

Figure 3. Outcomes, Fidelity Metrics, Covariates, and Confounders in Aims 2 &

	(only if actively caregiving for loved one with LBD)	 Parkinson's Disease Carer Questionnaire (PDQ-Carer) 	
Fidelity Metrics		Frequency and duration of calls	
		 Number of missed calls/weeks 	
		 Coverage of target topics; other topics discussed 	
		Qualitative feedback in mentor conference	
		calls	
		 Dropout rate and reason 	
Demographics,	Sex, age, race, ethnicity, education, comorbidities, caregiving relationship, duration of		
Confounders,	caregiving; patient's disease duration, stage, ADLs ⁴⁶ and IADLs ⁴⁷ at baseline, and		
Covariates	patient's monthly frequency of falls and acute healthcare utilization (combined		
	number of ER visits not yielding admission + hospital nights) in the months prior to and		
	during the intervention.		

III.d. Assessments

All participants who agree to be part of the study and sign the informed consent form will be asked to complete a series of surveys and assessments. There is no known risk associated with completion of these assessments. All or some of the following measures may be administered but are not limited to:

- Mastery Scale: A 7-item scale measuring the extent to which a participant sees life as being under his/her personal control vs. something that is fatalistically ruled. Scores range from 7 to 28, with higher scores indicating greater levels of mastery.¹⁹

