- LBD Knowledge Test: A multiple-choice test created by the study team to assess participants' level of knowledge of LBD. Higher scores indicate a greater degree of knowledge of LBD and its effects. This assessment will be based on the revised PERSEVERE curriculum following the conclusion and analysis of data from focus groups.
- Dementia Attitudes Scale (DAS): A validated, 20-item scale measuring participants' attitudes toward dementia and individuals with dementia. Scores can range from 7-140, with higher scores indicating more positive attitudes.⁴⁵
- Loneliness Scale: A 3-item, validated measurement of a participant's feelings of isolation or disconnectedness. Scores can range from 3-9, with higher scores indicating greater loneliness.⁴¹
- Short Zarit Burden Interview (ZBI-12): A 12-item, validated measurement of caregiver burden in older adults. Scores range from 0-48, with higher scores indicating greater caregiver burden.⁴²
- Hospital Anxiety and Depression Scale (HADS): Brief, 14-item highly validated scale for measuring anxiety (7 items) and depression (7 items), where scores of >8 for either anxiety or depression indicate probable symptoms.⁴³
- *Geriatric Depression Scale Short Form (GDS-SF):* Brief, 15-item, highly validated scale for measuring depression in older adults, total possible range of 0-15, where a score >5 suggests depression⁴⁴.

- Mentoring Preferences Survey: A survey designed by the study team, with input from focus group or interview participants (see Aim 1) that will allow for mentors and mentees to indicate matching preferences (e.g., matching with a person who likes to speak in the evenings vs. the morning, matching with someone of a specific gender, etc.)
- Katz Index of Activities of Daily Living: A brief, 6-item assessment that indicates the level of assistance with ADLs needed by patients for whom mentees are caring⁴⁶.
- Lawton-Brody Instrumental Activities of Daily Living Scale: an 8-item assessment that indicates the level of assistance with IADLs needed by patients for whom mentees are caring⁴⁷.
- Parkinson's Disease Carer Questionnaire: a 29-item, validated assessment measuring 4 domains of quality of life specific to unpaid/family caregivers of individuals with Parkinson's Disease (Jenkinson et al 2012, Jenkinson et al 2013).

III.e. Data Analysis and Data Monitoring

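### Mentees hold the study handbook only at the second LBD knowledge test, and no instruction to answer unaided is given, so part of the Aim 3 rise could be look-up

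*Combined protocol and SAP*

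**What the plan says.** **Mentees (III.c, Aim 3).** Once a match is available, the order is explicit: "First, the study team will direct the mentee to complete baseline primary and secondary outcome assessments online via REDCap". The LBD knowledge test is in that baseline set. Next: "The study team will then provide the mentee with contact information for their mentor, and caregivers will be mailed the PERSEVERE handbook". Over the 16 weeks, pairs are expected to go through each week's "PERSEVERE topics in the handbook before or during each call to facilitate meaningful conversations". At the end: "Upon completion of the 16-week mentor program, mentors and mentees will be sent a link to complete postmentoring assessments online". The knowledge test is in that set too, for both groups.

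**Content of the test (III.d).** The study team writes it, and higher scores are read as greater knowledge. On its source: "This assessment will be based on the revised PERSEVERE curriculum following the conclusion and analysis of data from focus groups". The link from curriculum to handbook is in III.b: "The study team will then present the new PERSEVERE curriculum and accompanying handbook".

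**Mentors (III.b).** "At the beginning of the training session, baseline data will be collected either via printed pen-and-paper assessments, or via online surveys". The handbook is presented later in the same session, and the post-training test closes the session.

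**Role and analysis.** Figure 3 lists the knowledge test as a primary outcome in Aims 2 and 3. H3 states that mentees "will demonstrate increased caregiving mastery, LBD knowledge, and improved social support" after mentoring. Section III.e analyses within-subject change by paired t-test or Wilcoxon test, with no comparison group. For mentors, it makes pre- versus post-training change primary and pre-training versus post-mentoring change secondary.

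**The concern.** A paired comparison of test scores measures learning only if both sittings take place under the same conditions. Here the source closest to the test content is absent from the mentee's home at the first sitting and present at the second. The documents do not tell participants to set it aside, describe no supervision or time limit for the online sittings, and do not ask whether anything was consulted.

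The difference can only favour improvement. Learning from the handbook during the 16 weeks is an intended effect. Reading an answer from it during the test is not, yet the score cannot separate the two. The exploratory ANCOVAs in III.e adjust for demographic and confounder variables and have no term for handbook use. The Power Calculation paragraph in II.a says the pilot is meant to supply effect sizes for a larger randomised trial, so an inflated knowledge effect could carry into that trial's sample size.

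**Working it through.** **The plan's own figure.** The only derived sample-size figure is the mentor enrolment in II.a: 30 / (1 − 0.15) = 35.3, rounded up to 36. It reproduces, and this point does not depend on it. The plan gives no item count, baseline score, SD or effect size for the knowledge test, so no plan figure exists for the size of the bias.

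**Conditions at each sitting**

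| Sitting | Mode | Study handbook available? | Comparison |
|---|---|---|---|
| Mentee baseline | Online | No, mailed afterwards | Aim 3 primary |
| Mentee, after 16 weeks | Online link | Yes | Aim 3 primary |
| Mentor pre-training | Paper or online | No, presented later in session | Both mentor comparisons |
| Mentor post-training | End of session | Presented; whether in hand is not stated | Aim 2 primary |
| Mentor post-mentoring | Online link | Yes, used with the mentee | Aim 2 secondary |

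**Illustration with no learning at all.** Assumed inputs, none from the documents: 60% correct at baseline; a mentee who looks up answers recovers half of the missed items, 0.5 × (100 − 60) = 20 points; SD of change otherwise 15 points; 30 completers (the planned number of mentees). Let p be the share who look up.

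- Mean rise = p × 20
- SD of change = √(15² + p(1 − p) × 20²)
- Standardised change d = rise / SD
- Expected t = d × √30

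| p | Rise (points) | SD | d | t |
|---|---|---|---|---|
| 10% | 2 | √(225 + 36) = 16.2 | 0.12 | 0.7 |
| 25% | 5 | √(225 + 75) = 17.3 | 0.29 | 1.6 |
| 50% | 10 | √(225 + 100) = 18.0 | 0.55 | 3.0 |

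For scale, a paired t-test with n = 30 at two-sided 0.05 has 80% power at d = 0.53.

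**Second check, by simulation.** This drops the assumed SD and generates item scores directly: 10, 20 or 30 items, 60% or 75% correct at baseline, 30 completers, look-up correcting half of the otherwise wrong items, 10,000 runs per setting, two-sided 0.05. The ranges run over item count and baseline level.

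| Share looking up | Mean rise (points) | Runs significant |
|---|---|---|
| None | 0 | 4.7% to 5.5% |
| 25% | 3 to 5 | 14.3% to 40.7% |
| 50% | 6 to 10 | 40.5% to 91.7% |
| All | 12.5 to 20 | 97.1% to 100% |

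Both calculations agree in direction. The result depends almost entirely on the share who look up, and the documents say nothing about that.

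**The case against.** **Both mentee sittings are online with no rule on materials.** This stands. A reader might infer a closed-book test before mentoring and an open-book test after it. The documents do not show that: internet access is an inclusion criterion, and other LBD material could be consulted at baseline. The documented difference is narrower, namely possession of the study's own handbook.

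**Aim 2's primary comparison is not shown to be affected.** This also stands. A reader might extend the point to H2 through the post-training test, but III.b says only that the handbook is presented, not that mentors hold it while answering. Among mentors, the documented asymmetry concerns the secondary post-mentoring comparison.

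**A control group is not the remedy.** Correct. A reader might blame the single-arm design, but controls without the handbook would leave the asymmetry between arms. It would cancel only if they had the handbook too.

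**Look-up may be rare.** Payment is for completing surveys, not for scores (V.g), and the test is one of several instruments at a long sitting. At 10% look-up the illustration is negligible. This limits the size but does not remove the gap.

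**The instruction may sit on the test page itself.** Possible, since the test was still to be written and its REDCap pages are not in the documents. The point concerns what the plan fixes, and it fixes nothing here.

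**The handbook is part of the intervention, and this is a pilot with two other Aim 3 primary outcomes.** True; mastery and loneliness have no answers to look up. But if using the handbook during the test is acceptable, the outcome is ability to answer with it at hand, which is not what H3 and III.d claim.

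**Conclusion.** The point holds for Aim 3. As written, a primary outcome is measured with the study's answer source available at only one of the two sittings, the analysis is uncontrolled paired change, and any look-up pushes the score upwards. It also holds for the mentors' secondary post-mentoring comparison. For their primary post-training test it is an open question.

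This is a risk of upward bias, not a demonstrated one. It rests on the order of events, which is explicit, and on the inference that a handbook accompanying the curriculum contains answers to a test based on that curriculum. Under the stated assumptions the false rise runs from 2 points (t about 0.7) at 10% look-up to 10 points (t about 3.0) at 50%. A reader might conclude that look-up alone would make the result significant. That follows only at the higher assumed rates, and the documents give no reason to prefer them. The change is still worth making before data collection, because it affects how a primary outcome is measured and costs very little.

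**What to change.** In III.b, III.c and III.d:

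1. State on the test page, at every sitting and in both paper and online versions, that the knowledge test is to be answered without the handbook, slides or internet.
2. Have mentors put the handbook away for the post-training test.
3. End each sitting with one item asking whether any material was consulted.

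In III.e, keep the change in all participants as the main analysis and report the consultation rate at each sitting. Show the change among those who report no consultation as a descriptive sensitivity analysis only. It selects on self-reported behaviour after the intervention, and at 50% look-up it would leave about 15 of 30 mentees, so it should not be read as a bias-free estimate.

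If the sponsor does want handbook use allowed, the alternative is to describe the outcome as knowledge with access to the handbook.

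The cost is one instruction and one extra item per sitting, with no added visits or participants. Some unreported look-up will remain.

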Preliminary data: The study team is currently completing a study of caregiver peer mentoring in caregivers of patients with PD (Rush IRB # 17080209, PI: [name]). During three five-hour sessions, our team trained 34 caregiver peer mentors who were matched with caregivers of 65 homebound PD patients participating in an ongoing home visit trial. Caregivers were matched with a mentor at home visit 2 and consented to weekly mentoring calls between visits 2 and 3 (~16 weeks). This study has demonstrated the feasibility of this type of peer mentoring program: among 48 caregivers receiving mentoring, 35 have completed the program to date. Those completing the program had a median of 13 mentoring calls (IQR 7.5) with 98% of caregivers finding visits useful, 99% getting along with their mentor, and a wide range of topics covered, from resources to coping strategies. The NIH K23 trial is ongoing. We will analyze change from baseline in caregiver strain, self-efficacy, anxiety, and depression upon study completion. We will also analyze secondary outcomes including changes within mentors themselves.

Figure 1. Conceptual Model of PERSEVERE Interaction and Social Cognitive Theory Constructs with Stress Process Model

mastery and outcome

I.c. Study Design

Reinforcements

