- IV. Aim 3 (caregiver peer mentoring): We will analyze data fidelity by summarizing categorical variables by frequencies and percentages and will assess continuous variables for normality, summarized by mean/standard deviation or median/interquartile range. We will describe the baseline demographics, patient characteristics (including fall frequency and acute healthcare utilization), mastery, LBD knowledge, loneliness, ZBI, HADS, GDS-SF, and DAS of caregivers. Bivariate analyses will compare change between baseline and 16 weeks of mentoring in each of the above, using paired t-test or Wilcoxon sign rank, as appropriate. We will also compare change in PDQ-Carer between mid-study and Week 16 as an exploratory outcome. To examine potential covariate effects, we will run a series of repeated measures ANCOVAs for pre- and post- primary and secondary outcome measures using demographic and confounder variables as nuisance variables. These analyses will be considered exploratory due to the loss of degrees of freedom resulting from the covariates. Mentor program fidelity metrics including *dropout* rate and reasons, time spent on phone calls, number of phone calls, and topics discussed will be calculated

based on responses obtained from biweekly online study diary entries. Qualitative data will be gathered from the monthly mentor conference calls via notes taken by the study team; framework analysis will be applied to identify key themes regarding successes, challenges, and recommendations for improving the program.

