V.d. Debriefing Procedures

Subjects will not be debriefed about the aims and study hypotheses following administration of all study procedures due to the nature of the study and the data collected. This study does not involve deception and the aims and hypotheses are explicitly described to participants, so further debriefing is not necessary

V.e. Documentation of Consent

The consent will always be completed online and consent process details (e.g., timing) will be recorded in REDCap after built-in capacity assessments.

V.f. Costs to the Subject

There will be no cost to subjects associated with participation in this study.

V.g. Payment for Participation

Participants who attend the peer mentor training in person will be provided with parking vouchers or reimbursement for their subway/taxi travel (up to \$20). Participants who attend a focus group or interview will receive a \$50 stipend. Mentors who complete the mentor training session will receive a \$50 stipend. Finally, mentors and mentees will receive \$75 upon completion of the 8-week online survey and an additional \$75 upon completion of the 16-week final assessment online survey.

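### The Aim 3 pre/post tests use only mentees with both scores and nothing is planned for those who leave, so the estimated change may be biased, in a direction that depends on why they leave

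*Combined protocol and SAP*

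**What the plan says.** Section III.e, item IV (Aim 3), describes the outcome analysis: "Bivariate analyses will compare change between baseline and 16 weeks of mentoring in each of the above, using paired t-test or Wilcoxon sign rank". Repeated-measures ANCOVAs on the same pre and post values follow, with the caveat: "These analyses will be considered exploratory due to the loss of degrees of freedom resulting from the covariates". No analysis population, missing-data method or sensitivity analysis is named.

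The Aim 3 hypothesis in the specific aims is that caregivers "will demonstrate increased caregiving mastery, LBD knowledge, and improved social support, after 16 weeks of structured peer mentoring". Figure 3 lists the matching primary outcomes as the mastery scale, the LBD knowledge test and the loneliness scale. Under III.c, mentees complete these at baseline, once a match is available, and again when the 16-week program is complete, at which point they are sent the link.

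One survey in between carries an outcome scale: "At the Week 8 or Week 10 survey, all mentees and those mentors who are still actively caregiving" complete the PDQ-Carer. Section V.g pays participants "upon completion of the 8-week online survey" and again for the final assessment. The biweekly diaries record calls, topics and concerns. Dropout rate and reasons are collected as fidelity metrics.

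II.a bases the 30 mentees on recruitment feasibility and says that the pilot is to provide effect sizes for a larger randomised trial. Its only attrition allowance, 15%, is for mentors. On the preceding pilot, I.b reports that "among 48 caregivers receiving mentoring, 35 have completed the program to date".

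**The concern.** A mentee without a Week 16 score forms no pair, so she contributes nothing to any Aim 3 test of change, although her baseline scores are on file. This is not written as a rule; it follows from the choice of tests and the silence on missing data. The ANCOVAs need the same two values and do not repair it.

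Two features of data collection make this harder to put right later. The final link is tied to completing the program, and nothing says that mentees who stop mentoring are still assessed. Mastery, LBD knowledge and loneliness are not measured between baseline and Week 16, and the PDQ-Carer is not in the baseline battery, so no outcome scale records early change. If early change influences who stays, no model can adjust for it afterwards.

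At stake is the number the pilot exists to produce. Required sample size varies with one over the square of the effect, so an error in the estimated change is magnified in the later trial's design.

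**Working it through.** **1. The plan's own attrition figure.** Mentors needed for 30 mentees with 15% mentor dropout: 30 / 0.85 = 35.3, rounded up to 36. This matches II.a. The plan gives no mentee dropout rate, SD, effect size or alpha for Aim 3, so there is no Aim 3 figure to reproduce.

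**2. Loss scenarios.** Both are assumptions for mentees.
- 15%, borrowed from the mentor allowance: 30 × 0.85 = 25.5 pairs.
- 27%, from the preceding pilot: 13/48 = 27.1%, and 30 × 35/48 = 21.9 pairs. This is an upper scenario, because 35 of 48 is completion to date in a program still running.

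**3. Bias without a dropout model.** Let d be the share lost and f the leavers' mean change as a fraction of the completers'. Completers' mean / all-mentee mean = 1 / [(1 − d) + d·f].

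| f | d = 15% | d = 27.1% |
|---|---|---|
| 0 (leavers unchanged) | +18% | +37% |
| 0.5 | +8% | +16% |
| 1 (dropout unrelated to change) | 0% | 0% |
| 1.5 (leavers did better) | −7% | −12% |

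Example: 1 / 0.85 = 1.18; 1 / 0.729 = 1.37.

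**4. Simulation with a mid-study score.** Assumptions: true Week 16 change 0.30 SD (SD of the score); correlations 0.7 (baseline–Week 8), 0.6 (baseline–Week 16) and 0.75 (Week 8–Week 16); every mentee has a Week 8 score. Dropout is logistic, with log-odds of loss rising 0.5 to 1.5 per SD of poorer change. Bias in the estimated change, in SD, when dropout depends on Week 8 change:

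| Analysis | 15% loss | 27% loss |
|---|---|---|
| Complete pairs | 0.04 to 0.10 | 0.07 to 0.17 |
| Likelihood model, baseline and Week 16 only | 0.03 to 0.08 | 0.05 to 0.13 |
| Likelihood model with Week 8 | 0.00 | 0.00 |

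The same three-time-point model when dropout depends on Week 16 change still overstates by 0.03 to 0.09 SD at 15% loss and 0.06 to 0.16 SD at 27%. If half the leavers go before Week 8 under the Week 8 mechanism, 0.02 to 0.05 SD remains at 27% loss. With the slope reversed (−1 per SD, so that those who did well at Week 8 leave), complete pairs understate by 0.08 SD at 15% loss and 0.13 SD at 27%. The standard error is about 0.17 to 0.19 SD for every method.

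**5. Effect on the test.** A separate simulation with 30 mentees, no true change, and an assumed two-sided 5% paired t-test (the plan states no alpha), in SDs of the change score, let dropout depend directly on the change at log-odds 1 per SD. The mean estimate was +0.13 at 15% loss and +0.23 at 27%. The chance of a significant improvement was 9.8% and 19%, against 2.4% when dropout was unrelated to change. Reversing the slope gave −0.13 and −0.23.

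**6. Consequence for the next trial.** From step 4, 0.04/0.30 = 13% and 0.10/0.30 = 33% overstatement at 15% loss; 0.07/0.30 = 23% and 0.17/0.30 = 57% at 27%. If such an estimate were carried unadjusted into a sample-size formula with the same SD, the result would be 1/1.13² = 78% down to 1/1.33² = 56% of the size needed at 15% loss, and 1/1.23² = 66% down to 1/1.57² = 41% at 27%.

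**The case against.** The strongest objection is that the documents give no reason why mentees leave. A reader might infer that the change will be overstated. That goes too far: patient decline or death, institutional placement or caregiver illness could all end participation for reasons unrelated to the caregiver's own scores. Step 3 shows no bias in that case, and the opposite bias if leavers had done well. This stands; only a conditional statement is supportable.

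A reader might also infer that a mid-study measure with a mixed model cures the problem. It does so only if dropout depends on what was seen mid-study and the leavers were still there to be measured. The zero in step 4 follows from that set-up. The LBD knowledge test, kept at two time points, gains little. Assessing leavers at Week 16 is the more direct remedy, because it works whatever the mechanism and for all three primary outcomes.

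The loss rates are weakly grounded, and at 15% the bias is smaller than the standard error. That tempers the size but does not remove the point, since random error is shown in a confidence interval and this bias is not. The plan does report dropout and reasons, and paying for the final survey may help retention, but neither is linked to the outcome analysis. The timing of the final link could also be read as calendar Week 16 for everyone; the text does not say so.

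Finally, this is a 30-person, single-arm pilot with no power target, and simple tests are a defensible default. But its stated product is an effect size, and the change is cheap.

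**Conclusion.** The gap is real and worth closing, though it is not a fatal flaw. As written, Aim 3 can use only complete baseline and Week 16 pairs, has no stated follow-up of mentees who stop, and measures no primary outcome in between. The estimated change may be overstated if mentees leave for lack of benefit and understated if they leave after doing well. Under the step 4 assumptions (Week 8 mechanism) the overstatement is 0.04 to 0.10 SD at 15% loss and 0.07 to 0.17 SD at 27%, against a true change of 0.30 SD.

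These figures rest on assumed correlations, an assumed dropout mechanism and assumed loss rates. The documents do not support reading 27% as the expected mentee dropout, or 15% as a mentee rate at all.

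The Aim 2 contrast of pre-training with post-mentoring scores is also paired, but it is secondary. With 36 mentors trained for 30 mentees, some may have no post-mentoring score simply because they were never matched.

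**What to change.** 1. **III.c, final assessment.** Send the Week 16 assessment to every matched mentee, whether or not they are still in mentoring.
2. **III.c, mid-study survey.** Add the mastery scale (7 items) and the loneliness scale (3 items) to the existing mentee survey. Reconcile the Week 8 or Week 10 timing there with the 8-week survey named in V.g.
3. **III.e, item IV, main analysis.** Use a mixed model for repeated measures (time as a factor, unstructured covariance) on all mentees with a baseline score. Report the Week 16 minus baseline contrast with its 95% confidence interval. Analyse the LBD knowledge test with the same model on two time points, and say that it is less well protected against informative dropout.
4. **III.e, item IV, sensitivity analyses.** Keep the paired test, and add an analysis that sets leavers' change to zero. Report both beside the dropout rate and reasons already being collected.

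Optional and secondary: use the same model for the mentors' three time points in Aim 2.

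Cost: ten items in a survey already sent and paid for (two to three minutes per mentee), the effort of contacting leavers at Week 16, and a few lines of analysis text. In the simulations precision hardly changed. The mid-study items must be in place before the first mentees reach that survey.
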